10.1.3 Covariates and Subgroups

The relationship of clinical and baseline covariates to endpoints will be explored.

Categories for the covariates will be defined in the Statistical Analysis Plan. Baseline covariates include:

- Age
- Sex
- Race
- Stage at diagnosis
- IPI, aalPI, at diagnosis and secondary IPI, secondary aalPI at relapse
- Cell of origin (if available locally)
- Double and triple hit (if available locally)
- Refractory to frontline treatment
- Relapse within 1 year of diagnosis
- High-risk first complete remission
- MRD-positive at enrollment/MRD-positive within 6 months from enrollment/MRD-positive any time later during run-in.

10.1.4 Handling of Missing and Incomplete Data

Subjects missing post-baseline MRD assessments will be considered not to have achieved MRD-negative status.

10.2 Sample Size Considerations

This is a single-arm estimation study. It is assumed that an MRD-negative rate of 10% could be observed by chance in this study. Therefore, if the assumed rate of MRD negativity is at least 30%, then the sample size for this study (N = 30) is sufficient to demonstrate that, with 95% confidence, the rate of achieving MRD negativity is greater than 10%. This would also be sufficient to demonstrate evidence of clinical activity.

A table showing the CI for different assumed rates of MRD negativity with a sample size of N = 30 is presented below:

Assumed rate of MRD negativity, n (%)	Lower 95% Confidence Limit (%)	Upper 95% Confidence Limit (%)
8 (26.7)	12.3	45.9
9 (30)	14.7	49.4
11 (36.7)	19.9	56.1
12 (40)	22.7	59.4
14 (46.7)	28.3	65.7

The study will enroll approximately 90 subjects to achieve the desired sample size of 30 subjects who are MRD-positive at the time of enrollment or during the run-in period. As part of the run-in period subjects will be followed by clinic visits at 3, 5, 7, 9 and 12 months and thereafter every 3 months up to 24 months for monitoring of MRD status, it is therefore expected that there could be more than 30 subjects who at some point become MRD-positive before the study ends. Any subject who becomes MRD-positive after the 30 subjects required are treated will still be eligible for treatment with blinatumomab, therefore the final sample size may be higher than 30 subjects.

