The primary analysis set will include the first 30 subjects who received at least 1 dose of blinatumomab. The primary analysis set will be used for the primary analysis. The primary analysis will be triggered when the first 30 enrolled subjects have had the opportunity to complete cycle 1 of blinatumomab treatment.

The full analysis set will include all subjects who received at least 1 dose of blinatumomab. Subjects who were treated beyond the required sample size of 30 subjects will be included in this analysis set. The full analysis set will be used for the final analysis. The final analysis will be conducted when the subjects in the Primary Analysis Set have had an opportunity to complete the long-term follow-up visit 1 year from the first dose of blinatumomab.

Sample Size

This is a single-arm estimation study. It is assumed that an MRD-negative rate of 10% could be observed by chance in this study. Therefore, if the assumed rate of MRD negativity is at least 30%, then the sample size for this study ($N = 30$) is sufficient to demonstrate that, with 95% confidence, the rate of achieving MRD negativity is greater than 10%. This would also be sufficient to demonstrate evidence of clinical activity. For more detail see [Section 10.2](#).

Primary endpoint

MRD-negative rate is calculated as the number of subjects with MRD-negative status after treatment with blinatumomab divided by the total number of subjects in the respective analysis set. Exact binomial 95% confidence intervals (CI) will be used to analyze MRD-negative rate.

[figure not shown]
For a full description of statistical analysis methods, please refer to [Section 10](#).

Sponsor: Amgen Inc.

Data Element Standards
Version(s)/Date(s):

Version 5: 20 March 2015

Study Design and Treatment Schema

Footnotes defined on the next page

EOS = end of study; IP = investigational product; MRD = minimal residual disease; PET-CT = positron emission tomography/computed tomography

- ^a Run-in period is up to 24 months in duration. During the run-in period, enrolled subjects that are MRD-negative/PET-CT negative will be followed at 3, 5, 7 and 9 months and thereafter every 3 months (\pm 1 week) up to 24 months for monitoring of MRD status by next generation sequencing.

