10.4 Planned Methods of Analysis

10.4.1 General Considerations

Continuous variables will be summarized by the non-missing sample size (n), mean, standard deviation, median, first and third quartiles, minimum, and maximum.

Categorical variables will be summarized by the n and percentage in each category.

Time to event endpoints will be summarized with Kaplan-Meier (KM) curves, KM proportions at selected time points, KM quartiles (when estimable), the number of subjects with events, the number of subjects censored, and the pattern of censoring.

Point estimates for efficacy endpoints will be accompanied by 2-sided 95% CI including estimates of KM quartiles ([Brookmeyer and Crowley, 1982](#)), KM proportions ([Kalbfleisch and Prentice, 1980](#)), and binomial proportions ([Clopper and Pearson, 1934](#)).

No adjustments for multiplicity are planned for the analyses of the efficacy endpoints.

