10.4.2 Primary Efficacy Endpoint

MRD-negative rate at the end of cycle 1 of blinatumomab. MRD is defined as negative when the tumor clone sequence in plasma is below the assay's limit of detection (to be determined in the assay validation).

MRD-negative rate is calculated as the number of subjects with MRD-negative status after treatment with blinatumomab divided by the total number of subjects in the respective analysis set.

Exact binomial 95% CI will be used to analyze MRD-negative rate.

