3.2 Sample Size

This is a single-arm estimation study. It is anticipated that an MRD negative rate of 10% could be observed by chance in this study. Therefore, if the observed rate of MRD negativity is at least 30%, then the sample size for this study ($N = 30$) is sufficient to demonstrate that, with 95% confidence, the rate of achieving MRD negativity is greater than 10%. This would also be sufficient to demonstrate evidence of clinical activity.

A table showing the exact binomial confidence intervals for different observed rates of MRD negativity with a sample size of $N = 30$ is presented below:

Table 3-1. Confidence Intervals for Different Observed Rates of MRD Negativity With a Sample Size of 30

Observed rate of MRD negativity, n (%)	Lower 95% Confidence Limit (%)	Upper 95% Confidence Limit (%)
8 (26.7)	12.3	45.9
9 (30.0)	14.7	49.4
11 (36.7)	19.9	56.1
12 (40.0)	22.7	59.4
14 (46.7)	28.3	65.7

The study will enroll approximately 90 subjects to achieve the desired sample size of 30 subjects who are MRD positive at the time of enrollment or during the run-in period. As part of the run-in period, subjects will be followed by clinic visits at 3, 5, 7, 9 and 12 months and thereafter every 3 months up to 24 months for monitoring of MRD status, thus it could be more than 30 subjects who at some point become MRD positive before the study ends. Any subject who becomes MRD positive after the first 30 subjects with treatment of blinatumomab will still be eligible for treatment and included in Full Analysis Set. Therefore the final sample size may be higher than 30 subjects.

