9.1 General Considerations

Continuous variables will be summarized by the non-missing sample size (n), mean, standard deviation, median, first and third quartiles, minimum, and maximum.

Categorical variables will be summarized by the n and percentage in each category.

Point estimates for binomial proportions (eg., the primary efficacy endpoint) will be accompanied by 2-sided exact binomial 95% confidence intervals

([Clopper and Pearson, 1934](#)). Time to event endpoints will be summarized with Kaplan-Meier (KM) curves, KM proportions at selected time points, KM quartiles (when estimable), the number of subjects with events, the number of subjects censored, and the pattern of censoring. Point estimates of KM quartiles

([Brookmeyer and Crowley, 1982](#)) and KM proportions ([Kalbfleisch and Prentice, 1980](#)) will be accompanied by 2-sided 95% confidence intervals.

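### Does the protocol overstate what N = 30 can show by tying its claim to an assumed MRD-negative rate of 30%?

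*Protocol*

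**What the plan says.** Protocol Section 10.2 describes a single-arm estimation study and sets the reference rate: "It is assumed that an MRD-negative rate of 10% could be observed by chance in this study". It then says "if the assumed rate of MRD negativity is at least 30%, then the sample size for this study (N = 30) is sufficient" to show a rate above 10% with 95% confidence. The synopsis repeats the claim. The table beneath it in Section 10.2 gives confidence limits for 8, 9, 11, 12 and 14 of 30, under a column headed as assumed rates.

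SAP Section 3.2 carries the same argument and the same limits, but its condition reads "if the observed rate of MRD negativity is at least 30" percent, and its table title and column heading also say observed.

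The interval method is fixed. Protocol Section 10.4.1 says "Point estimates for efficacy endpoints will be accompanied by 2-sided 95% CI", Section 10.4.2 adds "Exact binomial 95% CI will be used to analyze MRD-negative rate", and SAP Section 9.1 has proportions "accompanied by 2-sided exact binomial 95% confidence intervals".

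Protocol Section 2.5 and SAP Section 2.2 give a clinical hypothesis of a rate above 10% and name 30% as a result worth having. SAP Section 2.2 adds that there will be no formal hypothesis test. Neither document gives a power or a probability that the lower limit will exceed 10%.

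**The concern.** An assumed rate in a sample-size section normally means the true rate used for planning. On that reading the protocol says that if the drug truly clears MRD in 30% of subjects, 30 subjects are enough to exclude 10%. Such a claim needs a probability, and none is given. The limits offered in support belong to results, not to true rates. The SAP then changes the word, which turns a planning claim into the reading of an interval, without comment.

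At stake is what a protocol reader believes about the design. A drug with exactly the 30% rate that the documents single out would leave 10% inside the interval more than a quarter of the time, and someone told that N = 30 suffices would not expect that.

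**Working it through.** **Inputs.** N = 30, reference rate 10% and rate of interest 30% (Protocol 10.2, SAP 3.2); two-sided 95% exact binomial interval (Protocol 10.4.1 and 10.4.2, SAP 9.1).

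**Step 1: reproduce the printed table.** For x of n, the Clopper-Pearson limits are the 0.025 quantile of Beta(x, n − x + 1) and the 0.975 quantile of Beta(x + 1, n − x).

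| x of 30 | Computed limits (%) | Printed limits (%) |
|---|---|---|
| 8 | 12.28 to 45.89 | 12.3 to 45.9 |
| 9 | 14.73 to 49.40 | 14.7 to 49.4 |
| 11 | 19.93 to 56.14 | 19.9 to 56.1 |
| 12 | 22.66 to 59.40 | 22.7 to 59.4 |
| 14 | 28.34 to 65.67 | 28.3 to 65.7 |

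All five rows agree to the printed decimal.

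**Step 2: find the smallest count that excludes 10%.** 7/30 has a lower limit of 9.93% and 8/30 has 12.28%. Equivalently, P(X ≥ 7 | 30, 0.10) = 2.58%, just above the 2.5% tail, while P(X ≥ 8 | 30, 0.10) = 0.78%. So 8 is the minimum, and it is the first row of both tables.

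**Step 3: test the sentence as the SAP words it.** An observed 30% is 9/30, with lower limit 14.7%, above 10%. Higher counts have higher limits. The sentence is true. It gives a sufficient condition rather than a threshold, so the fact that 8/30 also suffices does not contradict it.

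**Step 4: test it as a claim about the true rate.** The chance that the lower limit exceeds 10% is P(X ≥ 8 | 30, p):

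| True rate p | P(X ≥ 8) |
|---|---|
| 25% | 48.6% |
| 30% | 71.9% |
| 35% | 87.6% |
| 40% | 95.6% |

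At 30% the chance of not excluding 10% is 100 − 71.9 = 28.1%. The probability reaches 80% at a true rate of about 32.2% and 90% at about 36.1%. The chance of observing at least 9/30 when the truth is 30% is 56.8%.

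**Step 5: decide which reading the protocol supports.** Its column of assumed rates is expressed as n (%) and holds integers out of 30, each with its own confidence interval. A confidence interval is calculated from a result; a true rate has none. In that table, assumed can only mean a supposed result. The sentence above it uses the same word and makes sense in the same way, which is the sense the SAP spells out.

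**The case for a change.** The strongest case for a change is that the documents do more than estimate. They state a clinical hypothesis of a rate above 10%, justify N by its ability to demonstrate that, and call this evidence of clinical activity. A claim to demonstrate something invites the question of how often. The protocol answers that question for safety, where Table 8 gives stopping probabilities by true DLT rate, but not for efficacy. The 72% could also be generous. Protocol Section 10.1.4 counts subjects with missing MRD as not negative. If, as an assumption, 5%, 10% or 20% lack an assessment and the 30% applies to the rest, the probability falls to 66%, 59% or 43%. The SAP corrects the word without correcting the protocol.

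Part of this stands. The probabilities are right, they are absent from both documents, and they would inform a reader. But no printed figure is contradicted, because no power was claimed. The 72% applies at the lowest rate the sentence covers; at 35% and 40% the figures are 88% and 96%. The same N, reference rate and limits appear in both documents, so the single changed word clarifies one justification and does not substitute another. The loss from missing assessments depends on rates that neither document gives.

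**Conclusion.** No change follows. Taken literally as a statement about a true rate of 30%, the protocol sentence would be too strong, since the planned interval excludes 10% about 72% of the time. The table beside it and the SAP's wording show that a result of 30% is meant, and for that the claim is correct. What is left is a clerical slip in the protocol synopsis and Section 10.2, together with operating characteristics that the plan never claimed to provide.

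Nothing in the analysis depends on it. The primary result is a proportion with its exact two-sided 95% interval, calculated the same way under either word, and a reader of that interval sees directly whether 10% lies inside it. No success criterion, interim look or other decision rests on excluding 10%, and N stays at 30.

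This rests on the two-sided interval that both documents specify. A one-sided 95% exact bound would need 7/30 and give 84.0% at a true rate of 30%, but it is not planned and would not match the printed limits. It also rests on the study remaining one of estimation. If excluding 10% were later made a formal success criterion, its probability would have to be stated.

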3.3 Number of Subjects

Participants in this clinical investigation shall be referred to as “subjects”.

Approximately 90 subjects will be enrolled in the study. It is expected that approximately 30 subjects will be MRD-positive at screening or become MRD-positive during the 24-month run-in period. The number of subjects enrolled may be altered in order to ensure that approximately 30 subjects are assigned to treatment with blinatumomab. Enrollment may be stopped once approximately 30 subjects have been assigned to treatment with blinatumomab.

For sample size considerations see [Section 10.2](#).

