6.2.2 Study Stopping Rules

The DLT evaluation period will be the entire duration of cycle 1 of blinatumomab treatment. For subjects who are removed from study treatment for reasons other than an adverse event/toxicity, ie, disease progression, they will be considered DLT evaluable if they have received at least 7 days of the target dose of blinatumomab.

The occurrence of any of the following toxicities will be considered a DLT, if judged by the investigator to be related to blinatumomab administration:

- grade 5 toxicity
- grade 4 non-hematologic toxicity (non-laboratory)
- grade 4 hematologic toxicity lasting ≥ 7 days (**excluding lymphopenia**)
- grade 4 laboratory abnormalities lasting ≥ 7 days (**excluding lymphopenia**)
- any permanent discontinuation of blinatumomab as described in [Section 6.2.1.3](#)

The stopping rules will use a Bayesian approach to terminate the study if the posterior probability that the DLT rate is greater than 25% is $> 90\%$ ([Section 10.3.1](#)).

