10.1.2.5 DLT Analysis Set

A subject needs to meet 1 of the following criteria to be DLT evaluable:

- The subject experiences a DLT in the DLT evaluation period; OR
- The subject is removed from treatment for an adverse event/toxicity; OR
- The subject is removed from treatment for reasons other than an adverse event/toxicity, ie, disease progression, and the subject has received at least 7 days of the target blinatumomab dose; OR
- The subject does not experience a DLT and completes DLT evaluation period.

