10.3 Planned Analyses

10.3.1 Interim Analyses

Amgen will conduct evaluations of the ongoing DLT rate to assess if the threshold for early trial termination as defined in [Section 6.2.2](#) has been reached. The stopping rules use a Bayesian approach to terminate the study if the posterior probability that the DLT rate is greater than 25% is > 90%. The stopping boundaries assume a prior distribution of (0.50, 1.50) are presented in [Table 7](#) and the operating characteristics with pre-specified batch size of 10 new subjects per batch are presented in [Table 8](#). The

evaluations could occur more frequently if necessary to address emerging safety concerns. The operating characteristics in [Table 8](#) provide the probability of stopping the trial early for given hypothetical true DLT rates, whereas the stopping criteria in [Table 7](#) are based on situations where the empirical evidence would result in a posterior probability of $\geq 90\%$ that the true DLT rate is $\geq 25\%$.

Table 7. Stopping Boundary With Posterior Probability of 90% and DLT Limit of 25%

Number of DLT evaluable subjects (inclusive)	Stop study if observing these many DLTs
10	≥ 5
20	≥ 8
30	Study completes

DLT = dose limiting toxicity

Table 8. Operating Characteristics With Batch Size of 10 Subjects

True DLT rate	Probability of stopping	Average sample size
0.20	5%	30
0.25	14%	28
0.30	27%	26
0.35	44%	24
0.40	62%	21

DLT = dose limiting toxicity

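### The DLT boundary and operating-characteristics tables describe a study that ends at 30 evaluable subjects, while the plan allows dosing beyond 30 with no stated maximum

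*Protocol*

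**What the plan says.** **Treatment past 30.** Protocol Section 10.2 says: "Any subject who becomes MRD-positive after the 30 subjects required are treated will still be eligible for treatment with blinatumomab". SAP Section 3.2 says the same and places these subjects in the Full Analysis Set. No upper limit is given. Closing enrollment is optional: "Enrollment may be stopped once approximately 30 subjects have been assigned to treatment with blinatumomab" (Protocol Section 3.3). Subjects already in the run-in, which lasts up to 24 months, can still convert and be treated.

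**The stopping rule.** Protocol Section 6.2.2 would "terminate the study if the posterior probability that the DLT rate is greater than 25% is" above 90%. Section 10.3.1 adds the prior: "The stopping boundaries assume a prior distribution of (0.50, 1.50"). Neither passage limits the number of subjects to which the rule applies. The Data Review Team (DRT) looks at DLTs at every 10th subject or every 6 months, whichever is earlier (Protocol Section 10.3.2, SAP Section 7.2), again with no end at 30.

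**The tables.** Protocol Table 7 and SAP Table 7-1 say to stop at 5 or more DLTs among 10 evaluable subjects and at 8 or more among 20. At 30 they say "Study completes". Of Table 8 the protocol says the "operating characteristics with pre-specified batch size of 10 new subjects per batch are presented in" it. Table 8 and SAP Table 7-2 give average sample sizes that never exceed 30. SAP Section 7.2 says that continuous toxicity monitoring uses the boundary in Table 7-1.

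**The concern.** The tables stop where the plan does not. If more than 30 subjects are treated, reviews continue under a rule without a cap, but the table that SAP Section 7.2 names as the boundary has no count from 30 onward. A DRT holding 11 DLTs in 30 would find that the Section 6.2.2 criterion is met and that Table 7-1 reads as if the study were over.

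Two things are at stake. The first is whether subjects dosed after the 30-subject review are covered by a boundary that both documents state in the same way. The second is whether the printed operating characteristics describe the study that will be run.

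Dosing past 30 is plausible. As an illustration, suppose that 90 subjects enroll, enrollment is not closed early, and each subject independently has a 1/3 chance of treatment (the plan's own 30 of 90). The probability that more than 30 are treated is then about 45%.

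**Working it through.** **Inputs.** DLT limit 25% and posterior threshold 90% (Protocol Section 6.2.2). Prior (0.50, 1.50), read as a beta distribution because the family is not named (Protocol Section 10.3.1). Batches of 10 (same section). True DLT rates of 20% to 40% (Table 8).

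**Step 1: the boundaries.** After x DLTs in n evaluable subjects the posterior is Beta(0.5 + x, 1.5 + n − x). The boundary is the smallest x for which P(rate > 0.25) exceeds 0.90.

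| n | Smallest x | Posterior | Posterior at x − 1 | Printed |
|---|---|---|---|---|
| 10 | 5 | 0.935 | 0.812 | 5 or more |
| 20 | 8 | 0.913 | 0.814 | 8 or more |
| 30 | 11 | 0.908 | 0.826 | no count |
| 40 | 14 | 0.909 | 0.840 | no row |

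The two printed counts reproduce. The counts at 30 and 40 follow from the same criterion; they are not new thresholds.

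**Step 2: reproduce Table 8.** Let P1 = P(at least 5 DLTs in 10), and P2 = P(at most 4 in 10, and at least 8 in 20), from exact binomial probabilities. Stopping probability = P1 + P2. Average N with an end at 30 = 10·P1 + 20·P2 + 30·(1 − P1 − P2).

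At a true rate of 20%, P1 = 0.0328 and P2 = 0.0194. Stopping is 0.0522, and average N is 0.328 + 0.388 + 30 × 0.9478 = 29.15.

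| True rate | Stopping, computed | Stopping, printed | Average N, computed | Average N, printed |
|---|---|---|---|---|
| 20% | 5.2% | 5% | 29.15 | 30 |
| 25% | 13.7% | 14% | 27.85 | 28 |
| 30% | 27.3% | 27% | 25.77 | 26 |
| 35% | 44.5% | 44% | 23.06 | 24 |
| 40% | 62.3% | 62% | 20.10 | 21 |

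The stopping probabilities agree to within about half a point. The printed average sample sizes are the computed ones rounded up. Two alternatives fail to match. A look at 30 changes the stopping probabilities (Step 3). A maximum of 35 with no further look gives average N of 33.9/32.2/29.4/25.8/22.0. Table 8 is therefore the table of a study that ends at 30 with no DLT decision there.

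**Step 3: apply the existing criterion at 30.** Add P3 = P(at most 4 in 10, at most 7 in 20, and at least 11 in 30). The documents give no maximum, so 40 is assumed for average N: 10·P1 + 20·P2 + 30·P3 + 40·(1 − P1 − P2 − P3).

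| True rate | P3 (points) | Stopping, looks at 10/20/30 | Average N, maximum 40 (assumed) |
|---|---|---|---|
| 20% | 1.01 | 6.2% | 38.5 |
| 25% | 3.77 | 17.4% | 36.1 |
| 30% | 8.41 | 35.7% | 32.2 |
| 35% | 12.75 | 57.3% | 27.3 |
| 40% | 14.13 | 76.4% | 22.5 |

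With a further look at 40, stopping is 6.8% at a true rate of 20% and 20.0% at 25%. If every evaluable subject from 10 to 30 were a look, it would be 9.1% and 22.4%.

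**Step 4: who benefits.** Exposures avoided by the look at 30 = P3 × the number dosed after it. That number is not stated. For an assumed 3, 6 or 10, the average avoided is 0.03, 0.06 or 0.10 at a true rate of 20%, and 0.42, 0.85 or 1.41 at 40%.

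**The case against.** A reader might infer that subjects after the 30th are dosed with no stopping rule. The documents do not support that. The Section 6.2.2 criterion has no cap, Section 10.3.1 allows more frequent evaluations, the DRT reviews DLTs in all subjects, and SAP Section 7.1 repeats the criterion just before SAP Section 7.2. The DRT includes a biostatistician who can compute the posterior at any number. Its charter, which is not available here, may hold a fuller table. All of this stands. However, both documents leave only membership, procedures and meeting timing to the charter, and keep the boundary in their own text.

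A reader might also infer that Table 8 is wrong. It is not: it is correct for a study of 30, and giving operating characteristics at the planned size is ordinary. Its stopping probabilities remain right for the looks at 10 and 20. What fails is reading its average sample sizes, or its stopping probabilities over the whole study, as those of a trial that can run past 30 under a continuing rule.

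Two further inferences also fail. The documents do not confuse evaluable with treated subjects, because both boundary tables are headed as counting DLT-evaluable subjects. Nor is the rule undefined in the SAP, because the SAP refers to the protocol, which gives the prior.

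Finally, the practical effect may be small. The benefit reaches only subjects dosed after the look, and "The DLT evaluation period will be the entire duration of cycle 1 of blinatumomab treatment", which is 84 days. Some subjects beyond the 30th treated may already have started before 30 are evaluable. This also stands, and it is why the severity is low.

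**Conclusion.** The inconsistency is real and of low severity. The boundary and operating-characteristics tables in both documents describe a study capped at 30, whereas the sample-size sections, the posterior criterion and the review schedule have no cap. SAP Section 7.2 ties monitoring to a table with no count where the stated criterion is already met, at 11 of 30 and 14 of 40.

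Whether or not the criterion is applied at 30 changes the probability of stopping by 1.0 point at a true rate of 20% and by 14.1 points at 40%. The counts rest on reading the prior as beta, which the two printed counts support. Every average sample size above 30 rests on an assumed maximum, and the exposures avoided rest on an assumed number dosed after the look.

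**What to change.** Reconcile the passages, leaving the 25% limit and the 90% threshold as they are. Either of two routes would do:

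- Replace the "Study completes" row in Tables 7 and 7-1 with the counts that the existing criterion implies for reviews in tens while dosing continues (11 or more at 30, 14 or more at 40).
- Label Tables 7/7-1 and 8/7-2 as covering only the first 30 evaluable subjects, and state in SAP Section 7.2 that the Section 6.2.2 criterion governs later reviews.

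In either case, restate Table 8 and SAP Table 7-2, both stopping probability and average sample size, for the looks that will be made and a stated maximum.

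The cost is a sentence or a table row in each document and one rerun; no new data are needed. The downside is more stopping when toxicity is acceptable or at the limit. With a look at 30 it rises from 5.2% to 6.2% at a true rate of 20%, and from 13.7% to 17.4% at 25%. With a further look at 40 it reaches 6.8% and 20.0%, and more frequent looks raise it further, so the restated table should show the schedule actually intended.
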